## 9.7 Resistance Analyses

For all subjects, full length NS3/4A and NS5A from baseline samples will be sequenced by next generation sequencing (NGS). For subjects who experience virologic failure (on-treatment virologic failure or Relapseoverall as defined in Section 9.1), full length NS3/4A and NS5A from the first sample after virologic failure with HCV RNA  $\geq$  1000 IU/mL will be sequenced by NGS.

For all subjects who experience virologic failure for any reason, a listing by subject that includes HCV genotype/subtype, reason for non-response, baseline and post-baseline resistance data availability, and key baseline characteristics (e.g., sex, age, race, fibrosis stage, baseline HCV RNA ( $\log_{10}$ ), and treatment duration (days)) will be produced.

Only samples with an HCV RNA level of  $\geq$  1000 IU/mL will undergo sequence analysis in order to allow accurate assessment of products of amplification. Therefore, if the HCV RNA level at the time of HCV virologic failure or treatment discontinuation is < 1000 IU/mL, the sample closest in time after HCV virologic failure/treatment discontinuation with an HCV RNA level  $\geq$  1000 IU/mL will be used.

For each DAA target, signature amino acid positions and a key subset of amino acid positions for the respective inhibitor class are listed in Table 4. Appropriate subtype-specific prototypic reference sequences will be used for comparison with sequences from samples.

Target	Signature Amino Acid Positions	Key Subset of Amino Acid Positions
GT1 NS3	36, 43 (GT1a only), 54, 55, 56, 80, 107, 122, 132 (GT1a only), 155, 156, 158, 168, 170, 175 (GT1b only)	155, 156, 168 (all GTs)
GT2, 3, 4, 5, 6 NS3	36, 43, 54, 55, 56, 80, 155, 156, 166 (GT3 only), 168	
GT1 NS5A	24, 28, 29, 30, 31, 32, 54 (GT1b only), 58, 62, 92, 93	24, 28, 30, 31, 58, 92, 93
GT2, 3, 4, 5, 6 NS5A	24, 28, 29, 30, 31, 32, 58, 92, 93	(all GIS)

## Table 4.Signature Amino Acid Positions and the Key Subset of Amino Acid
Positions

The following definitions will be used in the resistance analyses:

- Baseline polymorphism: a polymorphism by NGS in a baseline sample at a detection threshold of ≥ 2% or ≥ 15% (depending on the threshold utilized) within a subject's viral population that was not present in the appropriate prototypic reference amino acid sequence for a given DAA target (NS3 or NS5A).
- Substitution at signature amino acid position: substitution (relative to reference) present at a detection threshold of ≥ 2% within a subject's viral population in a baseline or a post-baseline sample at a signature amino acid position.
- Post-baseline substitution: an amino acid substitution in a post-baseline time point sample that was not detected at baseline (< 2%) in the subject and is detectable in ≥ 2% of the sequences from the post-baseline sample.
- Enriched polymorphism: polymorphism present in both the baseline and a post-baseline sample whose prevalence in the post-baseline sample is at least 20 percentage points greater than the prevalence in the baseline sample [(post baseline % baseline %) ≥ 20].
- Treatment-emergent substitution: A post-baseline substitution or an enriched polymorphism.

The following will be provided:

- Listing by subject of all baseline polymorphisms at signature amino acid positions for each DAA target (NS3 and NS5A) at detection threshold of 2% for subjects in the ITT population.
- The number and percentage of subjects in the ITT population with baseline polymorphisms at signature amino acid positions at detection threshold of 2% and 15%. This table includes prevalence of each baseline polymorphism, and a summary of number of subjects with polymorphisms in NS3 only, in NS5A only, any in NS5A, any in NS3 or NS5A, and any in NS3 + NS5A.

- The number and percentage of subjects in the ITT population with baseline polymorphisms at a key subset of amino acid positions in NS3 only, in NS5A only, any in NS3, any in NS5A, any in NS3 or NS5A, and any in NS3 + NS5A, by subtype, and total (across all subtypes).
- Listing by subject (and time point) of all treatment-emergent substitutions relative to the baseline amino acid sequences for each DAA target (NS3 and NS5A) for subjects in the ITT population who experience virologic failure.
- Listing by subject (and time point) of substitutions at signature amino acid positions (relative to reference sequence) for each DAA target (NS3 and NS5A) for subjects in the ITT population who experience virologic failure.

### HCV Genotype/Subtype

Phylogenetic analysis will be conducted on HCV NS3/4A and/or NS5A sequences from baseline samples from all subjects in order to accurately determine genotype/subtype. If the phylogenetic analysis is not available, then the result from Sanger sequencing of a region of NS5B by AbbVie or by the central laboratory will be used to determine the subject's HCV genotype/subtype, if available. Finally, if neither the phylogenetic analysis result nor the Sanger sequencing assay result is available, then the Inno-LiPA assay result from the central laboratory will be used to categorize the subject. This genotype/subtype category (referred to as final genotype/subtype) will be used in efficacy subgroup analyses.

In addition, the final genotype/subtype as well as the results from the central laboratory (Sanger sequencing or Inno-LiPA 2.0 Assay [if Sanger sequencing not available]) will be summarized as part of the baseline characteristics. A summary of HCV genotype subtype as provided by the central laboratory (Sanger sequencing or Inno-LiPA 2.0 Assay [if Sanger sequencing not available]) versus phylogenetic analysis also will be provided. Listings of HCV genotype and subtype will be provided separately for central laboratory results and phylogenetic analysis results.

#### 9.8 Patient Reported Outcomes

The following instruments will be used to collect PROs: EuroQol-5 Dimensions-5 Level (EQ-5D-5L) and Fatigue Severity Scale (FSS). Missing data for each measurement will be handled as described in Section 9.2.

The EQ-5D-5L is a health state utility instrument that evaluates preference for health status (utility). The 5 items in the EQ-5D-5L comprise 5 dimensions (mobility, self-care, usual activities, pain/discomfort, and anxiety/depression) each of which are rated on 5 levels of severity. Responses to the 5 items encode a discrete health state which is mapped to a preference (utility) specific for different societies. Subject's responses to the EQ-5D-5L will be combined into a unique health state using a 5-digit code with 1 digit from each of the 5 dimensions. The EQ-5D-5L states will be converted into a single preference-weighted health utility index score by applying weights. Subjects also rate their perception of their overall health on a separate visual analogue scale (VAS). The VAS score will be analyzed separately. Higher health index and VAS scores indicate better health. For EQ-5D-5L index and VAS scores, no imputation will be performed for missing items.

The FSS measures the impact of fatigue over the past week on specific types of functioning. The survey consists of 9 questions using a 7-point Likert scale. A total score is calculated as the average of the individual item responses (adding up all the answers and dividing by nine). Higher FSS scores indicate a higher degree of impact of fatigue. Imputation will be applied to the total score as described in Section 9.2. If a subject starts another treatment for HCV, then all PRO values for this subject measured on or after the start date of the new HCV treatment will be excluded from analyses.

Summary statistics (number of subjects and mean) at each protocol-specified visit and for the change from baseline (number of subjects, mean, SD, minimum and maximum) to each applicable post-baseline timepoint will be provided for EQ-5D-5L health index score and VAS score and for the FSS total score.

The following analysis of PROs also will be performed:

• Number and percentage of subjects who have ever experienced a decrease from baseline up through each applicable time point of greater than or equal to 0.7 in the FSS total score will be calculated along with a two-sided 95% CI based on Wilson's score method.

## 10.0 Safety Analyses

## 10.1 General Considerations

Safety data will be summarized for the Safety Analysis Set.

## 10.2 Adverse Events

Adverse events (AEs) will be summarized and presented using primary MedDRA System Organ Classes (SOCs) and preferred terms (PTs) according to the version of the MedDRA coding dictionary used for the study at the time of database lock. The actual version of the MedDRA coding dictionary used will be noted in the AE tables and in the clinical study report. Specific AEs will be counted once for each subject for calculating percentages, unless stated otherwise. In addition, if the same AE occurs multiple times within a subject, the highest severity and level of relationship to GLE/PIB will be reported.

Participants in clinical trials with HIV-1 may develop infections typically associated with acquired immune deficiency syndrome (AIDS). Adverse events that are considered to be AIDS-associated opportunistic infections (OIs) as identified by the investigators on the AE eCRF will not be included in any analyses of AEs as they will be summarized separately (see Section 10.2.6).

Adverse events and AIDS-associated OIs will be summarized for the following groups: adolescents (age < 18 years), adults (age  $\ge$  18 years), and overall.

#### **10.2.1** Treatment-Emergent Adverse Events

Treatment-emergent AEs are defined as any AE with an onset date that is after the first dose of study treatment and no more than 30 days after the last dose of study treatment. Events where the onset date is the same as the study treatment start date are assumed to be treatment-emergent. If an incomplete onset date was collected for an AE, the event will be assumed to be treatment-emergent, unless there is other evidence that confirms that the event was not treatment-emergent (e.g., the event end date was prior to the study treatment start date).

### 10.2.2 Adverse Event Overview

An overview of AEs will be presented consisting of the number and percentage of subjects experiencing at least one event for each of the following AE categories:

- Any treatment-emergent AE;
- Treatment-emergent AEs with a "reasonable possibility" of being related to DAAs (GLE/PIB);
- Treatment-emergent AEs of Grade 3 or higher;
- Serious treatment-emergent AEs;
- Serious treatment-emergent AEs with a "reasonable possibility" of being related to DAAs (GLE/PIB);
- Treatment-emergent AEs leading to discontinuation of study treatment;
- DAA-related treatment-emergent AEs leading to discontinuation of study treatment;
- Treatment-emergent AEs of Grade 3 or higher with a "reasonable possibility" of being related to DAAs (GLE/PIB);
- Serious treatment-emergent AEs leading to discontinuation of study treatment;
- Treatment-emergent AEs leading to interruption of study treatment;
- Treatment-emergent AEs leading to death;
- Deaths.

The following listings of AEs will be prepared:

- All serious AEs (from the time the subject signed the study-specific informed consent through the end of the study);
- Treatment-emergent serious AEs;
- Treatment-emergent AEs leading to death;
- Treatment-emergent AEs leading to discontinuation of study treatment;
- Treatment-emergent AEs leading to study treatment interruption.

## 10.2.3 Treatment-Emergent Adverse Events by SOC and/or PT

The number and percentage of subjects with treatment-emergent AEs will be tabulated by primary MedDRA SOC and PT. The SOCs will be presented in alphabetical order, and the PTs will be presented in alphabetical order within each SOC.

Subjects reporting more than one AE for a given PT will be counted only once for that term (most severe/highest grade incident for the severity tables and most related incident for the relationship tables). Subjects reporting more than one AE within a SOC will be counted only once for that SOC. Subjects reporting more than one AE will be counted only once in the overall total.

The following summaries of AEs by SOC and PT will be generated:

- Treatment-emergent AEs;
- Treatment-emergent AEs with a "reasonable possibility" of being related to DAAs (GLE/PIB);
- Serious treatment-emergent AEs;
- Serious treatment-emergent AEs with a "reasonable possibility" of being related to DAAs (GLE/PIB);
- Grade 3 or higher treatment-emergent AEs;
- Treatment-emergent AEs of Grade 3 or higher with a "reasonable possibility" of being related to DAAs (GLE/PIB);

- Treatment-emergent AEs leading to discontinuation of study treatment;
- DAA-related treatment-emergent AEs leading to discontinuation of study treatment;
- Serious treatment-emergent AEs leading to discontinuation of study treatment;
- Treatment-emergent AEs leading to interruption of study treatment;
- Treatment-emergent AEs leading to death.

A listing of treatment-emergent AEs grouped by SOC and PT with subject numbers will be created.

The number and percentage of subjects experiencing treatment-emergent AEs will be tabulated according to PT and sorted by overall frequency. Similar summaries will be provided for Grade 3 or higher treatment-emergent AEs, DAA-related treatment-emergent AEs, DAA-related Grade 3 or higher treatment-emergent AEs, and DAA-related treatment-emergent serious AEs.

Treatment-emergent AEs and DAA-related treatment-emergent AEs will be summarized by maximum severity grade level of each PT, where each AE will be assigned a grade level (Grade 1, 2, 3, 4, or 5) by the investigator. Additionally, of the subjects who reported at least one treatment-emergent AE, the number and percentage of subjects reporting events with a maximum severity of Grade 1, Grade 2, Grade 3, Grade 4, and Grade 5 will be calculated.

Treatment-emergent AEs also will be summarized by maximum relationship of each PT to study treatment (DAAs), as assessed by the investigator.

### 10.2.4 SAEs (Including Deaths) and Adverse Events Leading to Study Treatment Discontinuation

SAEs (including deaths) and AEs leading to study treatment discontinuation will be summarized by SOC and PT and in listing format as described in Section 10.2.2 and Section 10.2.3.

## 10.2.5 Adverse Events of Special Interest

For the hepatic decompensation/hepatic failure AE of special interest defined below, the number and percentage of subjects experiencing at least one treatment-emergent AE in the search will be presented overall and by SOC and PT. In addition, a listing of treatment-emergent AEs for subjects meeting the search criterion will be provided. For the hepatocellular carcinoma AE of special interest, a listing of all AEs meeting the search criterion will be provided.

Hepatic decompensation and hepatic failure:

- Treatment-emergent events only
- Product MedDRA Query (PMQ) of "Hepatic decompensation and hepatic failure"

Hepatocellular carcinoma:

- All post-baseline cases, treatment-emergent and non-treatment emergent
- Search based on specific MedDRA PTs of hepatocellular carcinoma, hepatic neoplasm, hepatic cancer, hepatic cancer metastatic, and hepatic cancer recurrent.

### 10.2.6 AIDS-Associated Opportunistic Infections

The number and percentage of subjects experiencing treatment-emergent AIDS-associated OIs will be tabulated according to SOC and PT for the HCV/HIV co-infected subjects. Subjects reporting more than one AIDS-associated OI for a given PT will be counted only once for that term. Subjects reporting more than one AIDS-associated OI within a SOC will be counted only once for that SOC. Subjects reporting more than one AIDS-associated OI within a SOC will be counted only once in the overall total. A listing of treatment-emergent AIDS-associated OIs will also be generated.

#### 10.3 Analysis of Laboratory Data

The hematology (including coagulation parameters), clinical chemistry, urinalysis (specific gravity and pH only), and total insulin laboratory tests defined in the protocol operations manual will be summarized.

The baseline value for clinical laboratory tests will be the last non-missing measurement on or before the day of the first dose of study treatment. Values on Day 1 must also be before the time of first dose if time is available. The same baseline value will be used for change to Treatment Period visits and change to Post-Treatment Period visits.

Each laboratory variable will be summarized for all protocol-specified time points (starting with Baseline) with the number of non-missing observations, mean and standard deviation, median, Q1 and Q3 of inter-quartile range, minimum and maximum. Mean change from baseline to each applicable visit, including applicable post-treatment visits, will also be summarized for the laboratory parameters of ALT, AST, bilirubin (total, direct, and indirect), and alkaline phosphatase, with the number of observations, baseline mean, and visit mean. The change from baseline mean, standard deviation, median, Q1 and Q3 of inter-quartile range, minimum and maximum will be presented for the mean change from baseline.

Changes in hematology (including coagulation parameters), clinical chemistry, and urinalysis laboratory parameters will be tabulated using shift tables. Laboratory data values will be categorized as low, normal, or high based on the normal ranges of the laboratory used for each sample. A shift table from baseline to minimum value and maximum value during the Treatment Period will be created. In this shift table, the number and percentage of subjects with baseline values within or above the normal range (baseline high or normal) and a minimum value below the normal range (post-baseline low) and the number and percentage of subjects with baseline values within or below the normal range (baseline low or normal) and a maximum value above the normal range (post-baseline high) will be summarized.

Summaries of graded laboratory parameters and shift from baseline grade (see below) will be summarized for the following groups: adolescents (age < 18 years), adults (age  $\ge$  18 years), and overall.

The laboratory parameters listed in Appendix B will be assigned a toxicity grade of 1, 2, 3, or 4. The number and percentage of subjects with a maximum toxicity grade of 1, 2, 3 or 4 will be summarized for the baseline value and for values during the Treatment Period for subjects with both a baseline value and at least one post-baseline value during the Treatment Period. To be counted, the post-baseline value must have a toxicity grade that is more extreme than the toxicity grade corresponding to the baseline value. The summary will also include the number and percentage of subjects with a maximum of at least Grade 3 for all laboratory parameters in Appendix B. A listing of all relevant laboratory parameters will be provided for each subject who had an increase to Grade 2 or higher for any laboratory variable in Appendix B.

Shift tables from baseline to maximum value during the Treatment Period will be created for ALT and total bilirubin values categorized by toxicity grade. For each baseline grade, the frequency and percentage of subjects with maximum Grades of 0, 1, 2, 3, and 4 during treatment will be calculated. The number and percentage of those subjects who improved from baseline, were the same as baseline, or who worsened from baseline will also be calculated.

Shift tables from baseline to the Week 4 and Final Treatment Visits will be created for ALT and total bilirubin categorized by toxicity grade. For each baseline grade, the frequency and percentage of subjects with Grades of 0, 1, 2, 3, and 4 at the Week 4 and Final Treatment Visits will be calculated. The number and percentage of those subjects who improved from baseline, were the same as baseline, or who worsened from baseline will also be calculated.

#### Assessment of Hepatic Laboratory Values

The number and percentage of subjects with laboratory values meeting the following criteria during treatment will be summarized for adolescents (age < 18 years), adults (age  $\ge 18$  years), and overall:

- Post-nadir (preceding value is lower than the subsequent value) ALT > 5 × ULN (regardless of grade change);
- Total bilirubin ≥ 2 × ULN and > baseline (i.e., a post-baseline value must be more extreme than the baseline value to be considered);
- Post-nadir ALT > 3 × ULN and total bilirubin > 2 × ULN;
- Post-nadir ALT > 3 × ULN and total bilirubin  $\leq$  2 × ULN.

Four listings (one for each bullet above) of all liver function tests including ALT, AST, total, indirect and direct bilirubin, ratio of direct to total bilirubin, and alkaline phosphatase values will be provided for each subject who met the criterion defined above.

### Hepatic Laboratory Abnormalities of Interest

Among the events assessed under "Assessment of Hepatic Laboratory Values," the following criteria are of interest:

- Confirmed post-nadir  $ALT > 5 \times ULN$ ;
- Post nadir ALT > 3 × ULN and a concurrent total bilirubin > 2 × ULN with a direct bilirubin:total bilirubin ratio > 0.4.

To support the assessment of hepatic laboratory abnormalities of interest, the following potential events will be summarized for adolescents (age < 18 years), adults (age  $\ge 18$  years), and overall:

- Confirmed post-nadir ALT > 5 × ULN;
- Post-nadir ALT > 3 × ULN and total bilirubin > 2 × ULN with a direct bilirubin:total bilirubin ratio > 0.4.

Two listings (one for each bullet) of all liver function tests including ALT, AST, total, indirect and direct bilirubin, ratio of direct to total bilirubin, and alkaline phosphatase values will be provided for each subject who met the criterion defined above.

The assessments of hepatic laboratory values and hepatic laboratory abnormalities of potential interest will include subjects who have a baseline and at least one post-baseline value during the Treatment Period for the respective parameter. Criteria that include both ALT and total bilirubin require both parameters to have a baseline and at least one value during the Treatment Period. The maximum ratio relative to the ULN will be used to determine if subjects meet any of the criteria listed above. The ALT and total bilirubin values do not need to be concurrent in order to meet the defined criteria in statistical summaries. For ALT, the post-baseline value must represent an increase from the first nadir (including baseline) to be counted. First nadir is defined as the last value prior to the first increase. For total bilirubin, a subject will be counted if the post-baseline laboratory value meets the above criteria regardless of the baseline laboratory value (i.e., the post-baseline laboratory value does not need to be worse than the baseline laboratory value), except where noted in the criteria above. A confirmed post-nadir increase in ALT is defined as two consecutive values of  $ALT > 5 \times ULN$  after nadir, either both during treatment or at the final treatment measurement and the next consecutive post-treatment measurement. A single post-nadir ALT value of greater than  $5 \times ULN$  followed by lost to follow-up (no additional ALT values) also will be considered as confirmed (i.e., will not require confirmation). The ratio of direct to total bilirubin will be calculated using the same date/time sample corresponding to the total bilirubin elevation.

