3.5 Safety Endpoints

- Alanine aminotransferase elevations of National Cancer Institute (NCI) Common Terminology Criteria for Adverse Events (CTCAE) v4.03 Grade 1, 2, 3 or 4 with ALT grade increased from baseline for each subject in the Safety Analysis Set.
- Post-nadir ALT elevation > 3 × upper limit of normal (ULN) with total bilirubin > 2 × ULN for each subject in the Safety Analysis Set.
- Treatment-emergent hepatic decompensation/hepatic failure events for each subject in the Safety Analysis Set.
- Treatment-emergent AEs leading to discontinuation of study drug for each subject in the Safety Analysis Set
- Treatment-emergent SAEs for each subject in the Safety Analysis Set.

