Standard statistical, clinical, and laboratory procedures will be utilized in this study. All efficacy and safety-related measurements in this study are standard for assessing disease activity in subjects with acute HCV. All clinical and laboratory procedures in this study are standard and generally accepted.

Suitability of Subject Population

This study plans to enroll subjects age 12 years or older who have demonstrated evidence of acute HCV infection, who are either without cirrhosis or with compensated cirrhosis and are TN for the current HCV infection, in order to assess the safety and efficacy of GLE/PIB in the acute HCV patient population. Among people with acute HCV infection, PWID are the most prevalent population and PWID are at high risk of community transmission. Current intravenous drug users of the PWID population are eligible to participate in the study. Treatment of people who are at risk to transmit to other people leads to cost-savings for society.

Patients with acute hepatitis will likely have significant fluctuation of ALT levels and the peak ALT elevation can be > 10 times the ULN. In order to allow subjects with acute HCV infection to enroll, eligibility criteria are adjusted to reflect the characteristics of acute HCV infection.

Selection of Doses in the Study

The doses of GLE (300 mg) and PIB (120 mg) are the approved doses for treatment of chronic HCV infection and will be evaluated in the study for acute HCV infection. Acute HCV infection is generally benign compared with chronic HCV infection, and it is expected that the same dose of GLE/PIB (300 mg/120 mg) will be effective in treating acute HCV infection.

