• Negative anti-HCV antibody, HCV RNA and/or HCV core antigen followed by a positive HCV RNA or HCV core antigen all within an 11-month period prior to Screening; AND risk behavior for HCV infection within 6 months prior to positive HCV RNA or HCV core antigen;

OR

 Clinical signs and symptoms compatible with acute hepatitis (ALT > 5 × ULN and/or jaundice) in the absence of a history of chronic liver disease or other cause of acute hepatitis and positive HCV RNA or HCV core antigen all within an 8-month period prior to Screening; AND risk behavior for HCV infection within 6 months prior to positive HCV RNA or HCV core antigen;

OR

- Negative anti-HCV antibody with a positive HCV RNA or HCV core antigen within a 5-month period prior to Screening.
- 6. Negative test result for hepatitis B surface antigen (HBsAg).
- 7. No evidence of chronic HCV infection for this HCV infection.
- 8. No known active SARS-CoV-2 infection. All subjects should undergo viral testing to rule out SARS-CoV-2 infection at Screening. Subjects with active SARS-CoV-2 infection may only rescreen after they meet the following SARS-CoV-2 infection viral clearance criteria:
 - At least 10 days since first polymerase chain reaction (PCR) test result have passed in asymptomatic patients; or 10 days have passed since symptom onset and at least 24 hours since resolution of fever without use of antipyretics and other symptoms improvement.
- 9. Subject with HCV/human immunodeficiency virus 1 (HIV-1) co-infection must also meet the following criteria:
 - Naïve to HIV treatment:
 - Must have a cluster of differentiation 4 (CD4+) count ≥ 500 cells/mm³ (or CD4+ % ≥ 29%) at Screening;
 - Have no plan to initiate HIV-1 antiretroviral therapy (ART) treatment while participating in this study.
 - On a stable, qualifying HIV-1 ART regimen for at least 8 weeks prior to Screening:
 - Must have CD4+ count ≥ 200 cells/mm³ (or CD4+ % ≥ 14%) at Screening, and plasma HIV-1 RNA < 50 copies/mL at Screening (by the COBAS® Ampliprep/COBAS® Taqman HIV-1 Test, v 2.0).
 - The HIV-1 ART regimen must include at least 1 of the following:
 - Raltegravir orally (per os) (PO) twice a day (BID)
 - Dolutegravir PO QD or BID
 - Rilpivirine PO QD
 - Elvitegravir/cobicistat PO QD
 - Bictegravir PO QD

In addition to the above medications, subjects may take a nucleoside/nucleotide reverse transcriptase inhibitor backbone containing any of the following:

- Tenofovir disoproxil fumarate PO QD
- Tenofovir alafenamide PO QD

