### 3.4 Safety Endpoints

• ALT elevations of the National Cancer Institute (NCI) Common Terminology Criteria for Adverse Events (CTCAE) v4.03 Grade 1, 2, 3, or 4 during the Treatment Period with ALT grade increased from baseline for each subject in the Safety Analysis Set;

- Post-nadir ALT elevation > 3 × upper limit of normal (ULN) with total bilirubin > 2 × ULN during the Treatment Period for each subject in the Safety Analysis Set;
- Treatment-emergent hepatic decompensation/hepatic failure events for each subject in the Safety Analysis Set;
- Treatment-emergent AEs leading to discontinuation of study treatment for each subject in the Safety Analysis Set;
- Treatment-emergent SAEs for each subject in the Safety Analysis Set.

These endpoints, along with additional safety endpoints based on AEs, laboratory data, and vital signs are included in Section 10.2, Section 10.3, and Section 10.4, respectively.

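### The declared ALT-with-bilirubin safety endpoint can count a subject whose bilirubin is only falling from baseline, and the concurrent criterion that the SAP names as of interest has no planned count

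*SAP*

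**What the plan says.** Protocol 3.5 declares "Post-nadir ALT elevation" > 3 × ULN "with total bilirubin > 2 × ULN for each subject in the Safety Analysis Set". It gives no rule on timing or baseline. SAP 3.4 repeats the endpoint and adds the period: "with total bilirubin > 2 × ULN during the Treatment Period for each subject in the" Safety Analysis Set.

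The counting rules are in SAP 10.3, at the end of Hepatic Laboratory Abnormalities of Interest:

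- Timing: "The ALT and total bilirubin values do not need to be concurrent in order to meet the defined criteria in statistical summaries".
- Bilirubin against baseline: "the post-baseline laboratory value does not need to be worse than the baseline laboratory value", unless a criterion says otherwise. Under Assessment of Hepatic Laboratory Values, only the stand-alone bilirubin criterion says otherwise (≥ 2 × ULN and above baseline).
- The largest multiple of ULN decides whether a criterion is met.
- ALT must have risen from its first nadir, which is the last value before the first increase and may be the baseline value.

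The same part of the SAP says that "the following criteria are of interest" and lists, with the word concurrent underlined, post-nadir ALT > 3 × ULN and concurrent total bilirubin > 2 × ULN with a direct:total ratio > 0.4. The summaries planned in support of it, called potential events, omit that word.

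On the population, one of the four alternatives in eligibility criterion 5 (Protocol 5.1) is "Clinical signs and symptoms compatible with acute hepatitis", meaning ALT > 5 × ULN and/or jaundice, together with other conditions. Criterion 4 lists the excluding laboratory results and names neither ALT nor bilirubin. Protocol 4.2 says: "Patients with acute hepatitis will likely have significant fluctuation of ALT levels and the peak ALT elevation can be > 10 times the ULN".

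**The concern.** The two halves of the endpoint are treated differently. The ALT half has some protection against the natural course of the disease, because a value counts only if it follows a nadir. The bilirubin half has none: any on-treatment value > 2 × ULN counts, including one on its way down from a high baseline and one drawn before the ALT nadir. When bilirubin is falling, the maximum on-treatment multiple is the first one, which is the value closest to the acute episode. The ALT half is also easy to open, since a small rise from the first nadir is enough provided that the value is > 3 × ULN, and the protocol itself expects ALT to fluctuate.

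With a single arm there is no control rate to set against the count. SAP 10.5 carries it into the safety subgroups, and baseline bilirubin is not one of them, so no planned table separates the two sources of events. A subject counted this way also drops out of the companion row (post-nadir ALT > 3 × ULN with bilirubin ≤ 2 × ULN).

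**Working it through.** **The plan's own safety figure.** Table 1 gives the probability of at least one event as 1 − (1 − p)^283. For p = 0.5%, 1%, 2% and 3% this gives 75.8%, 94.2%, 99.7% and 100.0%. All four agree with the table. The point does not depend on them, but the same formula is used below.

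**The counting rule on constructed courses.** Chemistry is drawn at Baseline and Weeks 2, 4 and 8 (Protocol Appendix D). All values are in × ULN and are illustrative. Four rules are compared: the SAP rule; same visit only; bilirubin above baseline only; and same visit with bilirubin above its own lowest preceding value.

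| Course | ALT | Bilirubin | SAP | Same visit | Above baseline | Same visit, risen from nadir |
|---|---|---|---|---|---|---|
| 1 Resolving, small ALT rise | 30, 4.0, 4.1, normal | 6, 2.5, 1.0, normal | yes | no | no | no |
| 2 Resolving, late ALT rise | 20, 8, 3.2, 3.4 | 6, 2.5, 1.0, 0.8 | yes | no | no | no |
| 3 Resolving, early ALT rise | 12, 12.5, 4, 1 | 6, 4, 1.2, 0.8 | yes | yes | no | no |
| 4 Resolving, no ALT rise | 20, 8, 3.2, 1 | 6, 2.5, 1.0, 0.8 | no | no | no | no |
| 5 New injury | 4, 1, 6, 8 | 0.8, 0.7, 2.5, 4 | yes | yes | yes | yes |
| 6 New injury below a high baseline | 20, 4, 2, 9 | 6, 1.5, 0.9, 4 | yes | yes | no | yes |
| 7 New ALT rise, bilirubin high and flat | 20, 4, 10, 12 | 6, 5, 5, 5 | yes | yes | no | no |

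Course 1 in steps: the first ALT increase is from 4.0 (Week 2) to 4.1 (Week 4), so the first nadir is Week 2. The Week 4 value is post-nadir and > 3. The largest on-treatment bilirubin is 2.5 at Week 2, which is > 2. The endpoint is met although bilirubin fell at every visit. If direct bilirubin exceeds 40% of total at Week 2, the subject is also summarised as a potential event for the abnormality of interest.

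The table shows three things:

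- Courses 1 to 3 are counted by the SAP rule without any rise in bilirubin; course 4 is not counted.
- Requiring the same visit still counts course 3; requiring a value above baseline loses course 6.
- The last rule classifies courses 1 to 6 as intended but misses course 7, which the SAP rule keeps.

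**Size.** The documents give no rate, so both inputs are assumptions. Let j be the share of subjects with on-treatment bilirubin > 2 × ULN left over from the acute episode, and q the share of those with a post-nadir ALT > 3 × ULN. Expected events are 283 × j × q.

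- j = q = 5%: 283 × 0.0025 = 0.7 events; probability of at least one 51%.
- j = q = 10%: 283 × 0.01 = 2.8 events; probability 94.2%.
- j = q = 20%: 283 × 0.04 = 11.3 events; probability almost 100%.

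Each such subject adds 1/283 = 0.35 percentage points to the reported rate.

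**The case against.** The best defence is that the plan is a two-step screen. The SAP names the concurrent form as what matters, describes the looser summaries as potential events that support its assessment, and confines the non-concurrence rule to statistical summaries. For every subject who meets a criterion it lists ALT, AST, all bilirubin fractions, the direct:total ratio and alkaline phosphatase, so timing and direction can be read case by case. The protocol's definition says only that ALT is elevated with raised bilirubin, so the SAP does not contradict it, and the error is on the cautious side for safety. All of this stands. What it leaves open is that the declared percentage is not labelled as a screen and that the concurrent criterion gets no count.

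Three stronger readings are tempting, and the documents do not support them:

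- A reader might infer that resolving jaundice by itself is counted. It is not; course 4 shows that an ALT rise to > 3 × ULN is also needed.
- A reader might infer that the safety objective on ALT elevations cannot be met. ALT grade increase from baseline is its own declared endpoint. SAP 10.3 also plans ALT and bilirubin grade shift tables, a count of bilirubin ≥ 2 × ULN and above baseline, and a count of confirmed post-nadir ALT > 5 × ULN. The mixing is confined to the combined ALT-bilirubin counts.
- A reader might infer that raised bilirubin on Day 1 is to be expected. Jaundice is an and/or element in one of four alternative criteria, within an 8-month window before Screening, and may have resolved by Day 1. The absence of a ceiling makes raised bilirubin possible, no more.

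Replacing the declared endpoint with a same-date, rising-bilirubin rule would also go too far. On-treatment chemistry is drawn at only three visits, so a bilirubin peak that lags ALT can be missed, and course 7 would be lost.

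**Conclusion.** The point holds as a limited defect of definition. Under SAP 10.3 a subject whose bilirubin only falls can meet a declared safety endpoint, provided that ALT also rises from its first nadir to > 3 × ULN. The concurrent criterion that the SAP itself names as of interest has no planned count. That much follows from the text and needs no assumption.

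The frequency is unknown. The range of 0.7 to 11.3 events in 283 subjects rests wholly on the assumed 5% to 20% rates, and the documents do not say how many true events are expected either. The listings allow individual cases to be explained, but they do not change the reported percentage. A cheap addition to the tables is warranted; redefining the endpoint is not. The point concerns the analysis definition only, not clinical management.

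**What to change.** In SAP 10.3:

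1. Keep the existing non-concurrent count as the declared endpoint and sensitive screen. Add a footnote that it may include bilirubin elevation resolving from baseline.
2. Add a supplementary count of the criterion already named as of interest: post-nadir ALT > 3 × ULN with concurrent total bilirubin > 2 × ULN and direct:total ratio > 0.4.
3. Add a supplementary count of post-nadir ALT > 3 × ULN with total bilirubin > 2 × ULN on the same sample date, where bilirubin has risen from the subject's preceding bilirubin nadir. This is needed beside item 2, because concurrency alone still admits course 3 if its direct:total ratio exceeds 0.4.

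The cost is a few table rows from data already collected, repeated by age group and across the eight subgroup variables of SAP 10.5 if carried there. The supplementary counts are less sensitive when ALT and bilirubin peak at different visits, and item 3 also when bilirubin stays high and flat. That is why the broad count remains.
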